## 6 STUDY PARAMETERS

### 6.1 Efficacy Measures

#### 6.1.1 Primary Efficacy Measure(s)

- [REDACTED]

#### 6.1.2 Secondary Efficacy Measure(s)

- [REDACTED]
- [REDACTED]
- [REDACTED]
- [REDACTED]
- [REDACTED]

### 6.2 Safety Measures

- Visual Acuity (Early Treatment of Diabetic Retinopathy Study, ETDRS);
- Slit-Lamp Biomicroscopy;
- Cochet-Bonnet;
- Adverse Event Query;
- Dilated Fundoscopy;
- Intraocular Pressure.

## 7 STUDY MATERIALS

### 7.1 Study Treatment(s)

#### 7.1.1 Study Treatments/Formulations/Composition

- 1) 0.1% RGN-259 Ophthalmic Solution

2) Placebo Ophthalmic Solution (Vehicle for RGN-259 Ophthalmic Solution)

7.1.2 Instructions for Use and Administration

- At the end of Visit 1, qualified subjects will be randomized and the first dose of Study Drug will be administered in the Clinic. A 1-week supply of RGN-259 Ophthalmic Solution or Placebo Ophthalmic Solution will be dispensed to use 5 times per day;
- At Visits 2, 3 and 4, remaining/used study drug will be collected from subjects for drug accountability. Subjects will receive an additional 1 week supply of the same study drug they were previously randomized to (at Visit 1), to use 5 times per day for 1 week;
- At Visit 5, remaining/used study drug will be collected from subjects for drug accountability.
- Subjects will be instructed to use study drug on the day of applicable visits (Visits 2, 3, 4, and 5) prior to the visit.

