## SYNOPSIS

Protocol Title:	A Phase 3, Multi-Center, Randomized, Double Masked, Placebo Controlled Clinical Study to Assess the Safety and Efficacy of 0.1% RGN-259 Ophthalmic Solution for the Treatment of Neurotrophic Keratopathy (SEER-1)
Protocol Number:	RGN-NK-301
Investigational Product:	1) 0.1% RGN-259 Ophthalmic Solution 2) Placebo Ophthalmic Solution (Vehicle of RGN-259)
Study Phase:	3
Study Objective:	To compare the safety and efficacy of RGN-259 to placebo for the treatment of Neurotrophic Keratopathy (NK)
Overall Study Design:	
Structure:	Multi-center, double-masked, randomized, placebo-controlled study
Duration:	Approximately 6 weeks (43 days)
Controls:	Placebo Ophthalmic Solution (Vehicle of RGN-259)
Dosage/Dose Regimen/ Instillation/Application/Use:	Subjects eligible to be randomized will receive 1-2 drops of the following treatments to be administered in the affected eye(s) 5 times per day for 28 days (from Visit 1 to Visit 5). 1. 0.1% RGN-259 Ophthalmic Solution 2. Placebo Ophthalmic Solution Subjects will be randomized in [REDACTED] ratio [REDACTED]
Summary of Visit Schedule:	Seven visits over the course of approximately 6 weeks 
 
• Visit 1 = Day 1, Screening/Enrollment/Baseline
 
• Visit 2 = Day 8 ± 2 day, 1-Week Follow Up
 
• Visit 3 = Day 15 ± 2 day, 2-Week Follow Up
 
• Visit 4 = Day 22 ± 2 day, 3-Week Follow Up
 
• Visit 5 = Day 29 ± 2 day, 4-Week Follow-Up
 
• Visit 6 = Day 36 ± 3 day, 1-Week Post-Treatment Follow-Up
 
• Visit 7 = Day 43 ± 3 day, 2-Week Post-Treatment Follow-Up
 

Measures Taken to Reduce Bias:	Randomization will be used to avoid bias in the assignment of subjects to treatment, to increase the likelihood that known and unknown subject attributes are evenly balanced across treatment groups, and to enhance the validity of statistical comparisons across treatment groups. Masked treatment will be used to reduce the potential of bias during data collection and evaluation of clinical endpoints.
Study Population Characteristics:	
Number of Subjects:	Up to 100 subjects will be screened and approximately 46 subjects will be enrolled in this study [REDACTED] at approximately 20 clinical sites in the US.

Condition/Disease:
	
Neurotrophic Keratopathy

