#### 8.5 **Compliance with Protocol**

Subjects will be instructed on proper instillation and storage of study drug at the end of Visits 1, 2, 3, and 4 and given written instructions. Study

drug will be collected at each visit up to and including Visit 5 to assess dosing compliance. Dosing compliance will be based on the used vial count. If the subject uses [REDACTED] study drug during a dosing period, a subject will be deemed non-compliant and a dosing deviation will be recorded. These guidelines will be used by the Investigator for determining the subject's necessary compliance for the study and for recording deviations from this compliance.

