4.1 General Study Design

This is a Phase 3, multicenter, randomized, double-masked, placebo controlled safety and efficacy study. It consists of two treatment arms, a 0.1% concentration of RGN-259 ophthalmic solution and placebo ophthalmic solution, [REDACTED]. There are seven scheduled visits over approximately 6 weeks (43 days), with approximately 100 subjects being screened [REDACTED]. [REDACTED]. Visit 1 (Day 1) is the screening visit, as well as the baseline visit for subjects who are eligible for the study. Eligible subjects will be randomized to receive one of the two study treatments. Randomized subjects will then begin using study drug in the affected eye(s) 5 times per day for 28 days.

[figure not shown]
Study visits will be referred to in all tables and listings as the expected study day corresponding to the visit to enable reviewers to understand the assessment timing without referring to the protocol visit schedule. The following table shows the scheduled study visits, their planned study day (Day 1 corresponds to the day of randomization), and the acceptable visit window for each study visit:

Protocol RGN-NK-301/15-110-0006, SAP Version 1.0

Scheduled Visit	Planned Study Day	Visit Window
Visit 1	Day 1	n/a
Visit 2	Day 8	± 2 Days
Visit 3	Day 15	± 2 Days
Visit 4	Day 22	± 2 Days
Visit 5	Day 29	± 2 Days
Visit 6	Day 36	± 3 Days
Visit 7	Day 43	± 3 Days

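### Do one-week packs and ±2-day visit windows leave subjects without study drug?

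*Protocol*

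**What the plan says.** Protocol 7.1.2 governs dispensing. At Visit 1, "A 1-week supply of RGN-259 Ophthalmic Solution or Placebo Ophthalmic Solution will be dispensed to use 5 times per day". At the next three visits, "Subjects will receive an additional 1 week supply of the same study drug they were previously randomized to", for one more week at the same frequency. Leftovers do not carry over: "At Visits 2, 3 and 4, remaining/used study drug will be collected from subjects for drug accountability", and "At Visit 5, remaining/used study drug will be collected from subjects for drug accountability". Subjects are also expected to have drug in hand on the visit day: "Subjects will be instructed to use study drug on the day of applicable visits (Visits 2, 3, 4, and 5) prior to the visit".

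The Synopsis sets the windows. The first follow-up is "Visit 2 = Day 8 ± 2 day, 1-Week Follow Up", and Visits 3, 4 and 5 (Days 15, 22 and 29) carry the same ±2 days. SAP 4.1 repeats the windows and describes the regimen: "Randomized subjects will then begin using study drug in the affected eye(s) 5 times per day for 28 days". The Synopsis gives the same 28 days but equates them with the span between Visits 1 and 5.

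On adherence, Protocol 8.5 states that "Dosing compliance will be based on the used vial count". The threshold for calling a subject non-compliant is redacted there, and so is SAP 13.1 on dosing compliance. Protocol 10.5.1 says that each pouch holds five monodoses but not how many pouches make up a kit.

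**The concern.** The supply is fixed at one week, while the interval it must cover is not. A subject seen early at one visit and late at the next needs more than seven days of drug, and because leftovers are collected, an earlier short interval cannot make up the difference. Taken literally, the pack size, the windows and the regimen agree only on the nominal calendar.

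Two things would be at stake. Undosed days just before Visit 5, where healing is read for the primary endpoint, would dilute any drug effect. And if vial use were judged against days elapsed, a subject who used every vial and kept every window could be recorded as non-compliant. That might affect the per-protocol set.

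**Working it through.** **Inputs.** Visit 1 is Day 1 with no window. Visits 2 to 5 fall on Days 6–10, 13–17, 20–24 and 27–31 (Synopsis; SAP 4.1). Each of four dispensings covers 7 days at five instillations a day, so 35 instillations (Protocol 7.1.2). No carry-over. Assumption for the worst case: no spare days in a pack.

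**The plan's own figure.** 4 dispensings × 7 days = 28 days, and Day 29 − Day 1 = 28 days. The nominal schedule reproduces exactly.

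**Gaps allowed by the windows.** Shortest gap = earliest next visit − latest previous visit. Longest gap = latest next visit − earliest previous visit. Shortfall = longest gap − 7.

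| Interval | Shortest gap | Longest gap | Largest shortfall |
|---|---|---|---|
| Visit 1–2 | 6 − 1 = 5 | 10 − 1 = 9 | 2 days (10 instillations) |
| Visit 2–3 | 13 − 10 = 3 | 17 − 6 = 11 | 4 days (20 instillations) |
| Visit 3–4 | 20 − 17 = 3 | 24 − 13 = 11 | 4 days (20 instillations) |
| Visit 4–5 | 27 − 24 = 3 | 31 − 20 = 11 | 4 days (20 instillations) |

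**How many schedules are touched.** There are 5⁴ = 625 in-window date combinations. All gaps stay at 7 days or less only if no visit falls later in its window than the one before it, with Visit 1 at offset 0. That holds for 15 combinations, leaving 610 with at least one gap above 7 days. This counts combinations and is not a probability: the documents give no distribution of visit dates.

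**Two schedules in full.**
- Every visit two days late (Days 1, 10, 17, 24, 31): gaps 9, 7, 7, 7. Drug covers 7 + 7 + 7 + 7 = 28 days. There is a 2-day pause, but the planned 28 days of drug are supplied.
- Worst case (Days 1, 6, 17, 20, 31): gaps 5, 11, 3, 11. Drug covers 5 + 7 + 3 + 7 = 22 days. That is 30 − 22 = 8 uncovered days of those elapsed, or 28 − 22 = 6 days short of the planned regimen. It needs the early-then-late pattern twice.

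**Effect of spare drug in the pack (not stated in the readable text).** One spare day leaves maximum shortfalls of 1 day (first interval) and 3 days (later intervals); two leave 0 and 2; four leave none.

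**Apparent compliance of a subject who uses every vial.** Against a fixed 35 doses: 35/35 = 100%. Against actual days × 5: 35/45 = 77.8% for a 9-day gap and 35/55 = 63.6% for an 11-day gap. Which denominator applies is not visible.

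**The case for a change.** The strongest case for acting is that the conflict stands on unredacted text and does not need extreme dates. One visit falling a day later in its window than the visit before already makes an 8-day gap. Spare vials might remove the physical shortage, but not the conflict in wording, since Protocol 7.1.2 limits each later pack to one week of use and a subject on day 8 of a permitted interval has no consistent instruction. With only 18 subjects, each is 1/18 = 5.6% of the data, and the primary analysis is repeated in the per-protocol population (SAP 8.3).

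The wording conflict stands. The consequences are weaker. A shortage requires packs without spare days. Kit contents are not given, and the visit procedures (Protocol 8.3.1) and the scheduled and unscheduled visit sections (8.4.1, 8.4.2), where resupply could be described, are redacted. The non-compliance claim depends on a denominator that cannot be read, and the link to per-protocol membership on population definitions that are also redacted (SAP 8.1, 8.2). SAP 8.3 places efficacy analysis in the ITT population, with the per-protocol analysis as sensitivity only. The dispensing rule and windows are the same in both masked arms, so the expected effect of missed days is dilution, not a spurious advantage for the drug.

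**Conclusion.** No change to the plan. The supply wording, the windows and the two descriptions of treatment length do not agree away from the nominal calendar, and those passages would have to be reconciled if the protocol were used again; which of them should govern is not for a statistical review to choose. For this trial the question is closed: SAP 4.3 reports that the sponsor ended it for lack of enrolment after 18 subjects had enrolled and completed, and that it is no longer powered to detect differences. Changing the quantity dispensed can no longer alter any subject's exposure.

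What remains is detail that an analyst can supply: how many pouches were packed, which denominator was used for compliance, and, if packs held no spare days, which subjects had an interval longer than their supply. SAP 9.4 lists all study data by subject and visit, so this can be worked out from visit dates and vial counts. It is descriptive and changes no visible planned result.

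The possible size is at most 2 uncovered days in the first interval and 4 in a later one, with a worst case of 22 days of drug against 28 planned. These maxima assume exactly seven days per pack, no resupply between visits and visits at opposite edges of their windows. How often such dates occurred is unknown.

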**7.2 Other Study Supplies**

HCG urine pregnancy tests, Wratten #2 yellow filter, sodium fluorescein or BioGlo™ Fluorescein Strips, 1% Tropicamide, and Fluores.

**8 STUDY METHODS AND PROCEDURES**

**8.1 Subject Entry Procedures**

8.1.1 Overview

Subjects as defined by the criteria in Sections 5.2, 5.3, and 5.4 will be considered for entry into this study.

8.1.2 Informed Consent

Prior to a subject's participation in the trial (i.e., prior to changes in a subject's medical treatment and/or study related procedures), the study will be discussed with each subject, and subjects wishing to participate must give written informed consent using an informed consent form. The informed consent form must be the most recent version that has received approval/favorable review by a properly constituted Institutional Review Board.

8.1.3 Washout Intervals

Prohibited medications, treatments, and activities are outlined in the Exclusion Criteria (Section 5.4).

8.1.4 Procedures for Final Study Entry

Meet all inclusion and exclusion criteria.

8.1.5 Methods for Assignment to Treatment Groups:

At Visit 1, subjects who provide written informed consent will be assigned a unique 5-digit screening number, which includes the 2-digit site number plus a unique 3-digit screening number beginning with 001 (e.g., 11001, 11002, 11003, etc.). Screening numbers must be assigned in ascending consecutive order.

If all inclusion and exclusion criteria are met at Visits 1, each qualifying subject will then be assigned a 4-digit randomization number at the end of Visit 1. All randomization numbers will be assigned in strict numerical sequence and no numbers will be skipped or omitted. Assignment of qualified subjects to a treatment group will be accomplished by using a randomization code generated by an independent biostatistician. Investigators and study staff who will conduct the assignment procedure will be masked to the randomization code.

## **8.2 Concurrent Therapies**

The use of any concurrent medication, prescription or over-the-counter, is to be recorded on the subject's source document and corresponding electronic case report form (eCRF) along with the reason the medication was taken.

Concurrent enrollment in another investigational drug or medical device study is not permitted.

8.2.1 Prohibited Medications/Treatments

Disallowed medications/ treatments during the study are outlined in the Exclusion Criteria (Section 5.4).

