## 5.3 Inclusion Criteria

Subjects must:

- a. Be male or female of any race, at least 18 years of age at Visit 1.
- b. Have provided verbal and written informed consent;
- c. Be able and willing to follow instructions, including participation in all study assessments and visits;
- d. Have a persistent epithelial defect (a defect that has not reduced in size) for at least [REDACTED] with failure of conventional, nonsurgical treatment using non-preserved ocular lubricants, non-preserved topical ophthalmic antibiotics, oral doxycycline, patching, serum tears and/or therapeutic contact lenses at the time of Visit 1;
- e. Have stage 2 or 3 neurotrophic keratopathy (Mackie Classification) in at least one eye of which the longest dimension (length or width) of the defect [REDACTED] and which is confirmed not to be simply superficial punctate keratitis, at Visit 1;
- f. Have evidence of decreased corneal sensitivity [REDACTED] at Visit 1;
- g. Have at least one eye (the same eye) satisfy all criteria for d, e, f above
- h. If a female of childbearing potential, have a negative urine pregnancy test at Visit 1 and agree to use an adequate method of birth control throughout the study period. [Females are considered of childbearing potential unless they are surgically sterilized (bilateral tubal ligation, hysterectomy or bilateral oophorectomy) or post-menopausal (at least 12 months since last menses). Adequate birth control is defined as use of hormonal contraceptives (oral, implantable, injectable or transdermal), spermicide in conjunction with a barrier such as condom or diaphragm, or an intrauterine device (IUD), or surgical sterilization of partner. For non-sexually active females, abstinence may be regarded as an adequate method of birth control; however, if the patient becomes sexually active during the study, she must agree to use adequate birth control as defined above for the remainder of the study.]

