## 5.4 Exclusion Criteria

Subjects must not:

- a. Have any clinically significant slit lamp findings at Visit 1 that in the opinion of the investigator may interfere with the study parameters;

- b. Have significant blepharitis, meibomian gland dysfunction (MGD), lid margin inflammation or active ocular allergy that requires treatment at Visit1;
- c. Have a lid function abnormality (ex. Lagophthalmos) which, in the opinion of the investigator, is the primary cause of the persistent epithelial defect;
- d. Be diagnosed with ongoing ocular infection (bacterial, viral or fungal) or active inflammation (e.g. follicular conjunctivitis) not related to NK in the affected eye at Visit 1;
- e. Have had any ocular surgical procedure that is not considered the primary cause of NK in the affected eye within 2 months prior to Visit 1, or have any scheduled ocular surgical procedure during the study period;
- f. Have had any ocular surgical procedure that is considered to be the cause of NK within 4 weeks prior to Visit 1;
- g. Have received Botox injection for blepharoptosis within the previous 90 days in the affected eye;
- h. Have started the use of topical steroids in the affected eye in the previous 2 weeks or systemic steroids in the previous 4 weeks;
- i. Have used contact lenses (excluding therapeutic contact lenses) within 14 days prior to Visit 1 or anticipates use of contact lenses during the study period;
- j. Have an uncontrolled systemic disease that in the opinion of the investigator may interfere with the study parameters;
- k. Anticipate a change in immunosuppressive therapy during the course of the study;
- l. Have a known allergy and/or sensitivity to the study drug or its components;
- m. Be a woman who is pregnant, nursing or planning a pregnancy;
- n. Be unwilling to submit a urine pregnancy test at Visit 1, Visit 5 and Visit 7 (or early termination visit) if of childbearing potential;
- o. Be currently enrolled in an investigational drug or device study or have used an investigational drug or device within 30 days of Visit 1;
- p. Have undergone surgical treatments for NK including tarsorrhaphy or amniotic membrane graft within the previous 6 weeks in the affected eye;
- q. Plan to use serum tears in the affected eye during the study period.

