8.2.2 Allowed Concomitant Medications/ Treatments/ Procedures

Subjects who are taking antibiotic eye drops or ointments or non-preserved artificial tears for at least two weeks at the time of screening may continue to use them throughout the study at the discretion of the Investigator. However, these medications should not be started after the subject begins the study.

If a subject is taking one of the above listed allowed concomitant eye drops or ointments during the study the subject should be instructed to dose with the study eye drops first and wait at least 5 minutes before dosing with the other medication.

The use of these medications will be collected and recorded in the concomitant medications page of the eCRF.

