8.2.3 Escape Medications

At the discretion of the investigator, subjects may use topical steroid as an escape medication. Subjects receiving the escape medications will be exited, and will be counted as subjects who did not have complete healing of the epithelial defect in the primary efficacy analysis.

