8.2.4 Escape Surgical Intervention

At the discretion of the investigator, subjects may undergo surgical intervention (ex. tarsorrhaphy, amniotic membrane graft) to address their persistent epithelial defect. Subjects receiving surgical intervention will be exited, and will be counted as subjects who did not have complete healing of the epithelial defect in the primary efficacy analysis.

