4.3 Early Termination of the Study

Due to the rarity of the disease and the roughly 5 year enrollment period at multiple sites the Sponsor has decided to end this phase 3 trial based on the lack of enrollment. Even with the extended enrollment period, only 18 subjects were enrolled and subsequently completed the study. Analyses will be

Protocol RGN-NK-301/15-110-0006, SAP Version 1.0

conducted as originally intended; however, the study is no longer powered to detect statistical differences. See the revised power calculations in section 6.1 of this SAP.

As with other studies of rare diseases this study will focus on clinically meaningful difference. Clinically meaningful results will be assessed by the Sponsor’s medical and/or regulatory teams.

5. Study Treatments

The study treatments are 0.1% RGN-259 Ophthalmic Solution and Placebo Ophthalmic Solution (Vehicle).

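### Does leaving doxycycline, patching and therapeutic lenses unclassified on study mean that added care cannot be told apart from healing on study drug?

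*Protocol*

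**What the plan says.** Protocol 5.3(d) requires that conventional care has failed. The treatments it names are non-preserved lubricants, non-preserved topical antibiotics and, in its closing words, "oral doxycycline, patching, serum tears and/or therapeutic contact lenses at the time of Visit 1".

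For the study period, Protocol 8.2.1 gives no list of its own: "Disallowed medications/ treatments during the study are outlined in the Exclusion Criteria (Section 5.4"). In 5.4, item (q) rules out planned serum tears, and item (i) reads "Have used contact lenses (excluding therapeutic contact lenses) within 14 days prior to Visit 1 or anticipates use of contact lenses during the study period". Protocol 8.2.2 lets antibiotic drops or ointments and non-preserved artificial tears continue if already in use, and adds "However, these medications should not be started after the subject begins the study".

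Two added treatments have a stated effect on the endpoint. Under 8.2.3, "At the discretion of the investigator, subjects may use topical steroid as an escape medication"; such subjects leave the study and count as not healed. Under 8.2.4, "Subjects receiving surgical intervention will be exited, and will be counted as subjects who did not have complete healing of the epithelial defect".

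On recording, Protocol 8.2 requires any concurrent medication to be entered in the source document and eCRF "along with the reason the medication was taken". SAP 12.2 defines concomitant medication as either continued past the first dose or taken at any time after it. It tabulates the two together and also plans listings. SAP 9.4 lists all study data by subject and treatment. SAP 7 requires deviations to be identified and graded before the analyses are run, and SAP 8.3 repeats the primary analysis in the per-protocol population.

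**The concern.** The protocol treats added care as relevant to the endpoint. It scores topical steroid and surgery as not healed, bars new antibiotic drops and artificial tears, and excludes planned serum tears. Yet the readable lists leave three of its own 5.3(d) treatments unsettled. If a subject newly starts one of them and the defect closes by Visit 5, the readable text does not say whether that is a deviation or how the eye is scored. The SAP 12.2 table would not show it either, because new and continued use share one category.

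The small sample gives the point some weight. SAP 4.3 states that "only 18 subjects were enrolled and subsequently completed the study". Taken literally, with Protocol 8.6.1 defining a completer as someone not discontinued, nobody left for steroid or surgery. Added treatment without exit would then be the main readable route by which extra care could reach the result. The arms are masked and the gap is common to both, so the direction of any bias would depend on who received the treatment.

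**Working it through.** The plan gives no figure to reproduce: the allocation ratio, test, healing rates and power are redacted. The check is a comparison of text, then a size under stated assumptions.

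**Step 1. Each 5.3(d) treatment against the on-study lists.**

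| Treatment in 5.3(d) | On-study status in readable text |
|---|---|
| Non-preserved lubricants | 8.2.2 (as artificial tears): may continue, no new start |
| Topical antibiotics | 8.2.2: may continue, no new start |
| Serum tears | 5.4(q), through 8.2.1: planned use excluded |
| Therapeutic contact lenses | 5.4(i): exemption stands beside the 14-day limb and is not repeated for the study period, so two readings |
| Oral doxycycline | In neither 5.4 nor 8.2.2 |
| Patching | In neither 5.4 nor 8.2.2 |

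Three of the six are settled, one is ambiguous and two are unlisted. This part of the concern is correct.

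**Step 2. Can new use be separated from continued use?**

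- *Medication, including doxycycline.* A frequency table never identifies individuals; a listing does. Protocol 8.2 captures the drug and the reason, and SAP 12.2 and 9.4 produce listings by subject and treatment. SAP 12.2 cannot tell prior from concomitant use without timing relative to first dose, so that information must be held in some form. The readable text does not say that start dates are printed; this is an assumption. With it, a new start for the study-eye defect can be read off listings of 18 subjects.
- *Patching and lens wear.* These are not medications, and no recording route is readable. The visit procedures (Protocol 8.3.1), unscheduled and early-termination visits (8.4.2, 8.4.3) and examination appendix are redacted, so absence cannot be claimed.

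**Step 3. Is there a scoring rule?** The readable not-healed rules cover steroid and surgery only. The sections that would hold a wider rule are blacked out: populations, missing data, primary and sensitivity analyses in both documents. One safeguard is readable, the per-protocol repeat of the primary analysis in SAP 8.3, though whether such a subject would be excluded depends on a redacted definition.

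**Step 4. Size if one subject were rescored.** Assumptions: N = 18, two-sided Fisher exact test at 0.05, split 9:9 or 12:6.

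- One subject is 1/9 = 11.1 points at 9:9. At 12:6 it is 1/12 = 8.3 points (active) or 1/6 = 16.7 points (placebo).
- 9:9, active healer rescored: 6/9 v 1/9, p = 0.0498, becomes 5/9 v 1/9, p = 0.131.
- 9:9, placebo healer rescored: 6/9 v 2/9, p = 0.153, becomes 6/9 v 1/9, p = 0.0498.
- 12:6, active: 9/12 v 1/6, p = 0.043, becomes 8/12 v 1/6, p = 0.131. Placebo: 9/12 v 2/6, p = 0.141, becomes 9/12 v 1/6, p = 0.043.

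These examples were chosen beside the threshold. Over all outcomes, with assumed healing of 60% v 20% and binomial counts in each arm, rescoring one healer changes significance with probability 13.9% (active) or 20.4% (placebo) at 9:9, and 12.0% or 22.5% at 12:6.

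**Step 5. Effect on power.** Let added care heal a fraction u of those who would not otherwise heal, so p' = p + (1 − p)u. With u = 0.10, active becomes 0.60 + 0.40 × 0.10 = 0.64 and placebo 0.20 + 0.80 × 0.10 = 0.28.

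| Added care in | Power at 9:9 | Power at 12:6 |
|---|---|---|
| Neither arm | 28% | 27% |
| Both arms | 21% | 22% |
| Placebo only | 17% | 17% |
| Active only | 34% | 34% |

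Power is low in every row, and SAP 4.3 already says that the study is no longer powered and will be read for clinically meaningful difference.

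**The case for a change.** The strongest case for a change is that deviation status cannot be set consistently for a treatment on neither list, and SAP 7 wants that status settled before analysis. With 18 subjects, 11 points from one person matters to the estimate whatever the p-value. A split table and one sensitivity analysis would cost little.

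Part of this stands. The three treatments need a stated position when deviations are graded, and Protocol 5.3(d), 5.4(i), 8.2.1 and 8.2.2 must be reconciled by the sponsor. Which treatments belong on which list is not a matter for this review. But that writes down an existing policy and alters no analysis. Splitting the SAP 12.2 table would largely repeat what the listings of 18 subjects already show. The extra sensitivity analysis would be needed only if the redacted sections and the per-protocol repeat do not already deal with the case. It would leave the primary result as it is, and it would score some closed defects as unhealed, on account of an event that no passage shows to have happened.

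The inference that nobody left for steroid or surgery also rests on one narrative sentence in SAP 4.3, and cannot carry much weight.

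**Conclusion.** The omission is genuine but is missing detail that the analysts can fill from planned output. Two of the six treatments named in 5.3(d) are unlisted on study, one is ambiguous, and one table pools new with continued use. It does not follow that added treatment cannot be separated: for medication, the recorded reason and the subject listings supply what the table omits. For patching and lens wear, the readable text neither confirms nor excludes a record.

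The most that one subject could do is move an arm by 11.1 points at 9:9, or by 8.3 or 16.7 points at 12:6. The chance of a changed Fisher result is roughly one in eight to one in four under the assumed rates, in a trial whose power is about 28% at best without added care. No document shows that any subject started such a treatment. The conclusion rests on two assumptions: that the listings show start dates or equivalent timing, and that the sponsor settles the status of the three treatments when deviations are graded under SAP 7. On that footing, the primary analysis, the per-protocol repeat and the medication summaries can stand as planned.
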